1.1. List of Abbreviations

AE	Adverse Event
AHI	Apnea Hypopnea Index
APAP	Automatic Positive Airway Pressure
Bi-level PAP	Bi-level Positive Airway Pressure
CIA	Clinical Investigation Administration
CIP	Clinical Investigation Plan
CPAP	Continuous Positive Airway Pressure
CRF	Case Report Form
F&P	Fisher & Paykel Healthcare
GCP	Good Clinical Practice
HA	Hazard Analysis
IB	Investigators Brochure
ICF	Informed Consent Form
ICH	International Conference on Harmonization of Technical Requirements for Registration of Pharmaceuticals for Human Use
IRB	Independent Review Board
OSA	Obstructive Sleep Apnea
PAP	Positive Airway Pressure
SAE	Serious Adverse Event
UI	User Instructions

2. Document Information

2.1. Purpose and Scope

The purpose of the trial is to evaluate the performance, comfort and ease of use of the F&P full-face mask in the home environment in regards to satisfaction.

2.4. Monitoring Arrangements

F&P will be conducting the study, and as such the investigators will monitor the progress of the investigation. The principal investigator will have access to all source documents needed to verify the entries on the Case Report Forms (CRF) and other protocol- related documents; provided that participant confidentiality is maintained in agreement with local regulations. It will be the principal investigator's responsibility to inspect the CRF at regular intervals throughout the investigation, to verify the adherence to the protocol and the completeness, consistency and accuracy of the data being entered on them.

The investigator's file will contain the protocol/amendments, financial disclosure form, CRFs and data clarification and query forms, Independent Review Board (IRB) approval with correspondence, informed consent, staff curriculum vitae and authorization forms, screening and enrolment logs, and other appropriate documents/correspondence as per International Conference on Harmonization (ICH) and Good Clinical Practice (GCP) and local regulations.

2.5. Data Management

Data obtained for this investigation will be recorded in source documents and attached to the CRF for both the administration of the study and collection of participant data.

Original CRFs will be stored for 15 years by Fisher & Paykel healthcare. Copies of the CRF will be stored on site at North Texas Lung and Sleep Clinic for 15 years.

3. Investigator Information

4.2. Overseas Representative

5. Device Information

1. *What is the primary purpose of the study?* (check all that apply)

a. To describe the characteristics of a population
 b. To test a hypothesis
 c. To compare two groups
 d. To evaluate a treatment
 e. To predict an outcome
 f. To describe a process
 g. To evaluate a diagnostic test
 h. To compare three or more groups

5.2. Device Risk Analysis and Management

Positive airway pressure (PAP) therapy via a nasal or oronasal mask is standard clinical practice for patients with OSA. The risks associated with this treatment are limited to the potential for slight discomfort associated with the use of a full-face (ornonasal) mask during sleep. [REDACTED]

discomfort associated with the use of a full-face (breathable) mask during sleep.

[REDACTED]	[REDACTED]
[REDACTED]	[REDACTED]

6. Justification for a Clinical Trial

6.1. Synopsis

The investigation is a prospective, non-randomized, non-blinded study. This investigation is designed to evaluate the performance (leak and comfort) as well as participant's overall acceptance of the F&P full-face mask amongst participants with diagnosed OSA. A minimum of 40 participants with OSA currently using a full-face mask will be recruited by NTLSC (phone recruitment script is available in Appendix A).

This study will involve a baseline visit (Visit 1) where the participant's prescribed PAP therapy treatment settings will be gathered. An F&P ICON+ device will be issued to the participant (if required) during this visit as well as gaining their informed consent for the F&P full face mask trial.

Visit 2 will take place 7 ± 5 days after Visit 1. At this visit, participants will be fitted with the F&P full face mask as well as being asked a few questions in the form of a structured questionnaire. Initial impressions, comments and photographs will be captured via recorded audio and video (both with their consent). If the participant does not provide video and/or audio consent, written notes will be taken.

Visit 3 will take place 14 ± 5 days after Visit 2. The participants will come in for a final visit to return the trial mask and documentation and provide their feedback in the form of verbal comments and a structured questionnaire. Photographs will be captured as well as audio and video will be recorded during this visit (both with their consent). If the participant does not provide audio and/or video consent, written notes will be taken.

The mask and CPAP (if from the research pool) will be returned to NTLSC at the conclusion of the trial and the participant will return to their previous mask and mode of device treatment. This institution will recruit all participants within two weeks of beginning of the study.

If the participants prefer the F&P full face mask to their usual mask they will be invited to use the mask in-home for an additional 6 months. Monthly phone calls will be made and at the end of six months the participants will be asked to return the mask and continue using their usual mask.

[figure not shown]
This study will be conducted in accordance with ICH/GCP Guidelines. No deviation from the protocol will be implemented without the prior review and approval of the sponsor except where it may be necessary to eliminate an immediate hazard to a research participant. In such case, the deviation will be reported to the sponsor as soon as possible.

[figure not shown]
6.2. Literature Review

Obstructive Sleep Apnea (OSA) is a common sleep breathing disorder affecting up to 9% of the adult population¹ and is characterized by periodic collapse of the upper airway during sleep. The standard

[REDACTED]	[REDACTED]
[REDACTED]	[REDACTED]

treatment for obstructive sleep apnea is PAP, which consists of pressurized air applied to the nose via an interface. PAP includes continuous positive airway pressure (CPAP), automatic positive airway pressure (APAP) and Bilevel positive airway pressure (Bilevel PAP). Despite the effectiveness of PAP in abolishing upper airway obstruction, acceptance of and adherence with therapy has been sub-optimal^{2,3}. Reasons for the low compliance include nocturnal awakenings, incorrect therapeutic pressure and primarily discomfort due to poor mask fit. Poor mask fit can result in facial abrasion, leak causing fluctuations in therapeutic pressure and irritation of the eyes^{4,5}.

6.5. Justification for Administration

Participants will remain on their prescribed PAP pressure during the duration of the trial. Baseline PAP data on the participant's usual mask will be collected for 7 ± 5 days in order to evaluate leak measurements and efficacy of treatment compared to the investigational mask. Participants will not be randomised to use the F&P full face mask in-home for 14 ± 5 days.

7. Objectives of the Clinical Investigation

7.1. Hypothesis

[figure not shown]
[figure not shown]
Primary Objective:

[figure not shown]
- To evaluate the performance, comfort and ease of use of the F&P full face mask in a home environment in regards to the participants' view on overall comfort, overall experience and satisfaction.

Secondary Objective:

- To continue to evaluate the feedback of the F&P full face mask with users that preferred this over their usual mask (trial extension).
- To obtain 3D face scan data and head measurements from OSA participants in order to catalogue different facial structures for the use in the design of OSA interface masks.

7.3. Population

7.4. Risks

[figure not shown]
PAP therapy is standard clinical practice for patients with OSA. The risks associated with this treatment are limited to the potential for slight discomfort and pressure injury associated with the use of a full face mask during sleep. There will be no greater risk to participants in this trial as the site will be following routine practice for medical management of their patients. Participants in the study may benefit from receiving medical advice regarding their sleep disorders as well as regular medical follow-up.

7.5. Essential Requirements of the Relevant Directive

Essential requirements are not applicable since this study is being conducted in the USA only.

8. Clinical Investigation Design

8.1. Type of Investigation

8.4. End Points

8.4.1. Primary Outcomes

Primary Outcome:

- The F&P full face mask is easy to use, accepted by the participant and provides adequate treatment for OSA during in-home use measured via custom questionnaires and PAP data download.

8.4.2. Secondary Outcomes

- Seal performance as measured by leak measurements/PAP data.
- To obtain 3D face scanning and head measurements to assist with future product development.

8.5. Variables

Variable	Justification
Ease of use/Acceptability	To assess the ease of using the mask in the home and overall mask acceptability.
Mask Comfort	To assess the comfort (or lack of) of the mask as experienced by the participant while using it in-home.
Usability of the mask	To evaluate the usability of the F&P full face mask through a custom designed ease of use usability script
General Demographics	To gather participants general demographics
Preference	To assess which mask the participants prefers to use going forward.
Mask performance	To assess the mask's performance in relation to leak

Anthropometric Scans	To assist with future product development

8.6. Measurements

Refer to section 8.5 for measurements. The questionnaires as well as the sleep diary are included in the appendix B, C & D of this CIP document.

8.8. Inclusion / Exclusion criteria

Inclusion Criteria

- AHI ≥ 5 from the diagnostic night
- Aged 22 and over (FDA defined as default)
- Either prescribed APAP, CPAP or Bi-level PAP for OSA
- Existing Full-Face mask user
- Fluent in spoken and written English

Exclusion Criteria

- Inability to give informed consent
- Participant intolerant to PAP
- Anatomical or physiological conditions making PAP therapy inappropriate
- Current diagnosis of respiratory disease or CO₂ retention
- Pregnant or think they may be pregnant

[figure not shown]
[REDACTED]	[REDACTED]
[REDACTED]	[REDACTED]

[figure not shown]
[figure not shown]
[figure not shown]
8.9. Point of Enrolment

Participants will be recruited from patients who are prescribed either APAP, CPAP or Bi-level PAP for OSA at North Texas Lung and Sleep Clinic. The principal investigator (or those identified in delegation log) will ask the subjects whether they're interested to take part in the trial. The participants who provide informed consent and meet the inclusion/exclusion criteria will then be enrolled into the trial.

[figure not shown]
8.10. Patient Procedure

The study coordinator will ask the subjects whether they're interested to take part in the trial. Only eligible participants, that provide written informed consent, will be enrolled into the investigation.

[REDACTED]	[REDACTED]
[REDACTED]	[REDACTED]

[figure not shown]
[figure not shown]

[figure not shown]
Figure 1: Vitera Validation US In-Home Clinical Trial Procedure

[REDACTED]	[REDACTED]
[REDACTED]	[REDACTED]

[figure not shown]
With the following section, the days ($\pm N$) reflects: the date that will begin for that section (\pm the range within which the visit is acceptable)

[REDACTED]	[REDACTED]
[REDACTED]	[REDACTED]

[REDACTED]	[REDACTED]
[REDACTED]	[REDACTED]

[figure not shown]

8.14. Foreseeable Complications

From the MAUDE database, the common reported injuries from general CPAP and interface use are pressure sores, leading to cuts, rashes, skin abrasion and skin breakdown. Allergic reaction to the material of the mask can occur. Common complaints are discomfort and soreness on the areas of contact.

Participants on the trial are informed that they are able to switch back to their normal therapy if required. Adverse events will be noted in the individual's CRF.

9. Clinical Trial Documentation

STATISTICAL CONSIDERATIONS

[figure not shown]
9.5. Description of the Statistical Design

Since the trial is regarding the performance and acceptability of the trial device in order to inform product development, no statistical design is required.

[figure not shown]
[REDACTED]	[REDACTED]
[REDACTED]	[REDACTED]

9.6. Sample Size

From the 'Guidance for Industry and Food and Drug Administration Staff – Applying Human Factors and Usability Engineering to Optimize Medical Device Design' document issued on 3 February 2016, a number of 30 users will be sufficient to find a minimum of 97% of problems and on average can find 99% of all problems¹³. Additionally from previous experiences, a number of 30 users was not quite achieved when taking into account drop outs and no shows hence the recruitment drive for up to 45 participants has been set.

[REDACTED]	[REDACTED]
[REDACTED]	[REDACTED]
[REDACTED]	[REDACTED]

9.8. Statistical Termination

No interim analysis will be conducted as statistical outcomes will not change the conduct of the study.

9.9. Statistical Procedure Deviations

Statistical procedure deviations will be reported to the principal investigator and the sponsor. Deviations from the original statistical plan will be explained in the final study report.

9.10. Selection Criteria

All participants who consent, and are fitted with a mask that they attempt to sleep on will be included in the analysis. Please see section 8.10 for information on participant flow throughout the trial.

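### The only visible analysis set (Protocol 9.10) leaves mask-related fit failures and refusals at Visit 2 out of the denominator for overall acceptance

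*Protocol*

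**What the plan says.** Protocol 9.10 (Selection Criteria) gives the only analysis set in the visible text: "All participants who consent, and are fitted with a mask that they attempt to sleep on will be included in the analysis". It then refers to 8.10 for participant flow; most of 8.10 is not visible.

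Enrolment comes before fitting. Under 8.9 a person is enrolled on consent and eligibility. Under 6.1 the mask is fitted at Visit 2, 7 ± 5 days after Visit 1, and a questionnaire and first impressions are taken at that visit.

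Acceptance appears in three places, with different scope:

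- 6.1 (Synopsis) sets out to evaluate "overall acceptance of the F&P full-face mask amongst participants with diagnosed OSA".
- 8.4.1 (Primary Outcomes) asks whether the mask is "easy to use, accepted by the participant and provides adequate treatment for OSA during in-home use".
- 8.5 (Variables) justifies the row on ease of use and acceptability as "To assess the ease of using the mask in the home and overall mask acceptability".

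**The concern.** The 9.10 rule has three conditions: consent, being fitted, and attempting to sleep on the mask. The second and third can fail because of the mask itself. Someone for whom no adequate fit is found at Visit 2, or who sees the mask and will not try it, has given a clear negative answer on overall acceptance. Under 9.10 that person is not in the set, so inclusion depends in part on the outcome being summarised.

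At stake is the acceptance figure. Section 11 says the study is intended for internal use but allows the results to be used in marketing or regulatory documents, where the denominator of such a figure matters.

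**Working it through.** **1. Which outcomes the 9.10 set fits.** The primary objective is "To evaluate the performance, comfort and ease of use of the F&P full face mask in a home environment", and 8.4.1 is worded for in-home use. Ease of use at home, comfort, leak and PAP-download data cannot be scored without use. Acceptance during in-home use also presupposes use. For all of these the set is appropriate.

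**2. Where it does not fit.** Overall acceptance in 6.1 and overall acceptability in 8.5 carry no such restriction. The people lost are those enrolled and brought to Visit 2 who are not fitted or do not try the mask. Those who try it and later stop meet the 9.10 rule, remain in the set and are not part of this point.

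**3. Direction and size.** The protocol states no acceptance figure to reproduce. Let N be the number presented with the mask at Visit 2, k the number left out for mask-related reasons, and a the acceptance proportion in the 9.10 set.

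- Accepted count: a × (N − k)
- Proportion over all presented: a × (N − k)/N
- Overstatement: a − a × (N − k)/N = a × k/N

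This is never negative and is zero when k = 0. N is taken as 40 (minimum, 6.1) or 45 (upper recruitment figure, 9.6), supposing that everyone recruited reaches Visit 2. The values of a and k are assumptions.

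| k | N = 40, a = 0.8 / 0.9 | N = 45, a = 0.8 / 0.9 |
|---|---|---|
| 0 | 0 / 0 points | 0 / 0 points |
| 1 | 2.00 / 2.25 | 1.78 / 2.00 |
| 2 | 4.00 / 4.50 | 3.56 / 4.00 |
| 3 | 6.00 / 6.75 | 5.33 / 6.00 |

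Check in whole people, k = 2 and N = 40: 34/38 = 89.5% (exact 95% CI 75.2 to 97.1) against 34/40 = 85.0% (70.2 to 94.3). The intervals overlap widely, but the shift is always in one direction.

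**4. How likely it is to arise.** Let p be the assumed chance that a person presented with the mask is lost for a mask-related reason. The chance of at least one is 1 − (1 − p)^N, and the expected overstatement is a × p, whatever N is.

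| p | At least one, N = 40 | At least one, N = 45 | Expected overstatement, a = 0.8 / 0.9 |
|---|---|---|---|
| 0 | 0% | 0% | 0 / 0 points |
| 1% | 33.1% | 36.4% | 0.8 / 0.9 |
| 2% | 55.4% | 59.7% | 1.6 / 1.8 |
| 5% | 87.1% | 90.1% | 4.0 / 4.5 |

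The documents give no value for p.

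**The case against.** The strongest reply is that the set matches the outcome. Section 8.4.1 ties ease of use, acceptance and treatment together in one sentence about in-home use, and people who attempted to sleep on the mask are the natural population for it. This stands: a reader might infer that 9.10 is the wrong set for the primary outcome, and the documents do not support that. What remains is the wider wording in 6.1 and 8.5, which is why only a supplementary summary is needed.

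A reader might also infer that 9.10 conceals why people rejected the mask. It does not. Impressions and comments are collected at Visit 2, with written notes if recording is declined, and nothing in 9.10 forbids reporting them. Nor does the problem-finding rationale in 9.6 ("a number of 30 users will be sufficient to find a minimum of 97% of problems") add to the point, since a fit failure noted at Visit 2 is a problem found whatever denominator is used.

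Three further replies limit the point without removing it:

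- The visible text defines no acceptance proportion or threshold, so the bias exists only if acceptance is reported as a proportion.
- Every participant is an "Existing Full-Face mask user" and PAP-intolerant people are excluded, so failures before first use are probably few.
- Most of 8.10 is not visible, and a statistical plan (mentioned in 9.9) is not at hand; either may deal with these people. Even so, 9.10 itself fixes a rule, and it cites 8.10 for flow, not for the analysis set.

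**Conclusion.** The point holds in a narrow form and is minor. As written, the 9.10 rule leaves out consented participants who are not fitted, or do not try the mask, for mask-related reasons. For overall acceptance (6.1, 8.5) that makes the denominator too small. If acceptance is reported as a proportion, the error can only favour the mask.

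The size is unknown and may be zero. The figure of about 2 points per person at 40 to 45 participants rests on an assumed acceptance of 80-90% and on everyone recruited reaching Visit 2. It illustrates sensitivity and is not an estimate of what will happen. It would be tempting to conclude that the trial's acceptance result will be materially inflated; with no failure rate and no acceptance threshold in the protocol, that cannot be said.

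**What to change.** Keep the 9.10 set as the main set. Add one or two sentences to 9.10 to the following effect:

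- Overall acceptance will also be reported, as a supplementary summary, over all consented participants presented with the mask at Visit 2, with mask-related fit failure or mask-related refusal to try it counted as not accepted.
- The number and reasons will be given for everyone not fitted or not trying the mask.
- No-shows before Visit 2 and reasons unrelated to the mask will be listed separately and not counted as failures.

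Align this wording with the participant flow in 8.10.

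The cost is small: no extra participants, possibly one CRF line for the reason, a judgement on whether that reason is mask-related (best specified before the data are seen), and possibly a slightly lower acceptance figure.

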9.11. Statistical Data Management

Fisher and Paykel Healthcare may consult an external statistician to assist with the analysis of the data.

10. Adverse Events and Termination

An Adverse Event (AE) is any adverse change from the participant's baseline condition, i.e., any unfavourable and unintended sign or symptom or disease that occurs during the course of the study, whether or not considered related to the PAP treatment. All clinically significant AEs occurring during the study that were not present prior to the commencement of PAP treatment, will be recorded in the

[figure not shown]
[REDACTED]	[REDACTED]
[REDACTED]	[REDACTED]

CRF and source document and followed by the Investigator until resolution or stabilization occurs in accordance with GCP.

[figure not shown]
Serious AE's are considered to be AE's that result in any of the following outcomes, regardless of their relationship to the PAP treatment:

- Death
- A life-threatening AE
- In-patient hospitalization or prolongation of existing hospitalization
- A persistent or significant disability/incapacity
- A congenital abnormality/birth defect

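### Section 10 limits AE recording by an undefined start of PAP treatment, which does not match the baseline in its own AE definition

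*Protocol*

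**What the plan says.** The opening of Section 10 (Adverse Events and Termination) contains two adjacent sentences.

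- The definition: an AE is "any adverse change from the participant's baseline condition", which the same sentence restates as "any unfavourable and unintended sign or symptom or disease that occurs during the course of the study", whether or not it is thought related to PAP.
- The recording rule: "All clinically significant AEs occurring during the study that were not present prior to the commencement of PAP treatment, will be recorded" in the CRF and source document, and followed up.

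Other sections bear on these two:

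- Section 6.1 names Visit 1 as the baseline visit. The trial mask is fitted at Visit 2. A study PAP device is issued at Visit 1 only if one is needed.
- Section 6.1 also says that "participants with OSA currently using a full-face mask will be recruited", Section 8.8 lists "Existing Full-Face mask user" as an inclusion criterion, and Section 8.9 states: "Participants will be recruited from patients who are prescribed either APAP, CPAP or Bi-level PAP for OSA".
- Section 6.5 keeps each participant on the prescribed pressure throughout.
- Section 8.14 says that AEs are noted in the CRF, with no restriction on when the condition was first present.

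**The concern.** The definition measures change from baseline. The recording rule measures against the start of PAP treatment. That rule would suit a trial in which PAP is begun. Here PAP is already under way, and what changes is the mask. The visible text does not say which start is meant.

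Staff who follow Section 10 could therefore decide differently on whether the same worsening goes into the CRF. Section 8.14 lists rashes, skin breakdown and soreness at contact areas among the expected problems, and notes: "Allergic reaction to the material of the mask can occur". Skin and allergic conditions of this kind may well exist before the trial mask is fitted, whether from the usual mask or from before PAP. That is an assumption, since the protocol gives no prevalence. An event that is never recorded cannot be recovered at analysis, and the publication policy in Section 11 allows the results to be used in regulatory documents.

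**Working it through.** No arithmetic applies: the protocol states no AE rate, and the point depends on none. The check is to apply the recording rule to each kind of in-study adverse change and compare the result with the definition.

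**Step 1. Where is baseline?** Section 10 does not date the baseline condition. Section 6.1 calls Visit 1 the baseline visit, so Visit 1 is used here.

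**Step 2. When does PAP treatment commence?** Two meanings are possible.

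- *Literal:* the participant's first PAP use. Sections 6.1, 8.8 and 8.9 together place this before Visit 1 for every eligible participant.
- *Study start:* the start of study PAP (Visit 1) or of trial-mask use (Visit 2). Visit 2 follows Visit 1 by 7 ± 5 days, that is 7 − 5 = 2 to 7 + 5 = 12 days, so even this meaning leaves two candidate dates.

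**Step 3. What does AE refer to in the recording rule?** It may be the sign, symptom or disease, as the second half of the definition puts it, or strictly the change from baseline, as the first half puts it.

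**Step 4. Apply each reading.** All rows suppose a clinically significant worsening, recurrence or new event on the trial mask, so all meet the definition.

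| History of the condition | Literal start, AE = sign, symptom or disease | Study start, AE = sign, symptom or disease | AE = the change itself |
|---|---|---|---|
| First appears on the trial mask | Recorded | Recorded | Recorded |
| Arose on the usual mask, present at Visit 1, then worsens | Recorded | Need not be recorded | Recorded |
| Predates PAP, present at Visit 1, then worsens | Need not be recorded | Need not be recorded | Recorded |
| Predates PAP, absent at Visit 1, then recurs | Need not be recorded | Unclear: present earlier, but not at the start point | Recorded |

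**Step 5. Read the table.** In the last column the rule agrees with the definition throughout, because a change from the Visit 1 baseline cannot have been present before PAP or before the study. The clause then excludes nothing. In the other two columns it leaves out events that the definition includes. The rows are kinds of event and carry no information on how often each occurs.

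**The case against.** The strongest reply has four parts.

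1. *PAP treatment may mean the study treatment.* Section 10 judges relatedness of AEs and serious AEs against the PAP treatment, and relatedness is normally judged against the treatment under study. On that view the reference point is at or shortly after baseline. This is plausible, and for that reason the literal reading cannot be stated as fact. It does not cure the rule. A test of whether something was already present then leaves out worsening of any condition existing at the start, including injury from the usual mask. The term is also undefined, the prescribed pressure simply continues, and a device is issued only to those who need one.

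2. *The direct reading of AE is the change itself.* This stands. The defined term is a change from baseline, and on that reading nothing is lost. But the same definition goes on to equate an AE with a sign, symptom or disease, and the clause has an effect only if that second sense is used.

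3. *Section 8.14 has AEs noted without restriction.* This makes omission less likely in practice. It is also one more statement that does not match the recording rule.

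4. *Text not shown may settle it.* Part of Section 10 and most of the patient procedure are not available, and the CRF is not shown. A clarification there cannot be excluded.

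A reader might go further and infer that new events on the trial mask escape recording, or that a known share of AEs is lost. The documents support neither: new clinically significant events are recorded on every reading, and no AE figure is given. Nor does the clause turn stable usual-mask problems into AEs, since the definition still requires a change from baseline.

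**Conclusion.** The point holds as a minor inconsistency in safety recording. The recording clause in Section 10 uses an undefined reference point that does not match the baseline in its own definition and does not suit a population already on PAP. Depending on the reading, the clause excludes nothing, or leaves out worsening or recurrence of conditions that predate PAP, or leaves out worsening of any condition present at study start.

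The effect is narrow. It needs a pre-existing condition, a worsening or recurrence within the study, and staff who take one of the restrictive readings. No estimate or analysis population changes, and the number of events affected cannot be derived from the document.

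The conclusion assumes that baseline condition means condition at Visit 1, and that the part of Section 10 not shown does not already define the reference point.

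**What to change.** Reconcile the definition, the recording rule and the statement in Section 8.14 by replacing the clause with the protocol's own baseline. For example: *All clinically significant AEs that are new or worsened relative to the participant's baseline condition at Visit 1 will be recorded.* This works whichever meaning of PAP treatment was intended. The threshold of clinical significance and the follow-up wording stay as they are.

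An onset date on the CRF, if not already collected, would help to separate events before and after the Visit 2 mask fitting, but it is optional and not needed to remove the conflict.

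The cost is one sentence in Section 10, with no added visit or procedure. The downside is that slightly more events will be recorded.

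### Sections 8.14 and 10 set different thresholds for entering adverse events in the CRF, and under section 10 expected mask-contact harms can go unrecorded as AEs

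*Protocol*

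**What the plan says.** Section 10 (Adverse Events and Termination) opens with a wide definition. An AE is an adverse change from the participant's baseline, including "any unfavourable and unintended sign or symptom or disease that occurs during the course of the study", whether or not it is thought related to PAP. The next sentence gives the recording rule. It applies to "All clinically significant AEs occurring during the study" and is limited further to events "that were not present prior to the commencement of PAP treatment". Events that qualify are entered in the CRF and source document and followed up by the investigator.

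Section 8.14 (Foreseeable Complications) draws on a device-report database for CPAP and masks in general. It names pressure sores with resulting cuts, rashes, abrasion and skin breakdown, and mentions allergic reaction to the mask material. It adds: "Common complaints are discomfort and soreness on the areas of contact". Its recording rule has no threshold: "Adverse events will be noted in the individual's CRF".

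Two other sections describe the risk. The visible text of section 5.2 calls it "limited to the potential for slight discomfort associated with the use of a full-face" mask. Section 7.4 calls it "limited to the potential for slight discomfort and pressure injury associated with the use of a full face mask during sleep".

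**The concern.** A site needs one answer to the question of which events go on the AE page of the CRF. Section 8.14 answers all of them. Section 10 answers those that are clinically significant. The gap falls on skin and contact complaints, the harms most closely tied to the device under study.

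This matters for how the results are read. The study is non-randomized and non-blinded (section 6.1), every participant is to be fitted with the trial mask, and the sponsor conducts it (section 2.4). There is no concurrent control arm whose AE count could show that recording was incomplete. Section 11 allows the results to go into marketing or regulatory material. A count taken under the narrower rule could be quoted there as if it covered everything that meets the protocol's own definition.

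**Working it through.** There is no stated figure to reproduce. The check is a comparison of the rules, followed by one event taken through each of them.

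| Place | What it governs | Threshold for the event |
|---|---|---|
| Section 10, definition | What counts as an AE | None beyond being an unfavourable change from baseline |
| Section 8.14, last sentence | What is noted in the CRF | None |
| Section 10, recording sentence | What is entered in CRF and source and followed up | Clinically significant, and not present before PAP began |

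**Test event.** After fitting, a participant develops soreness or a slight abrasion under the mask. It was absent at baseline and before PAP was ever started. The assessor does not consider it clinically significant.

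1. Definition in section 10: it is an unfavourable sign or symptom, new since baseline, so it is an AE.
2. Section 8.14: it is an AE, so it is noted in the CRF.
3. Recording sentence in section 10: it is not clinically significant, so the sentence does not call for a CRF entry.

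The same event on the same form gets two answers. The event was chosen so that the clause on conditions present before PAP plays no part; the conflict arises from the significance filter alone.

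**Does another route capture it?** Mask comfort is a listed variable (section 8.5). There is a structured questionnaire with verbal feedback at Visit 3 (section 6.1), and section 8.6 refers to a sleep diary. Soreness and discomfort are therefore likely to be captured in part. That information is the participant's rating of the mask. It does not enter the AE count. The serious-AE list in section 10 does not close the gap either, because it is defined by outcomes such as death or hospitalization, which slight soreness or abrasion does not reach.

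**Size.** Let N be the number of contact-area AEs and s the share judged clinically significant. Section 8.14 yields N entries and section 10 yields s × N. The shortfall is (1 − s) × N, which runs from 0 when s = 1 to N when s = 0. The protocol gives neither N nor s, so no percentage can be defended.

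**Risk sentences.** Pressure injury appears in 7.4 but not in the visible part of 5.2. Allergic reaction appears only in 8.14. Both 5.2 and 7.4 use exclusive wording.

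**The case against.** The best defence is that the two rules work together: all AEs are noted under 8.14, and the clinically significant ones also receive source documentation and follow-up under section 10. Section 10 does not contain the word *only*, so the restriction is implied. That much stands. But section 10 names the CRF as well as the source document for the significant subset. If 8.14 already put every AE in the CRF, naming it again for a subset would be redundant. The joint reading is possible, but the text does not state it.

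Second, part of section 10, between its opening and 10.4, is not in the public text, and other parts are redacted. A definition of clinical significance, or a grading scheme, may be there, so its absence is not charged here. Such a definition would narrow the judgement but would not reconcile an unfiltered rule with a filtered one. The CRF and questionnaires are not visible either and may already prompt for skin events.

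Third, no visible passage makes an AE rate an endpoint, and discomfort has the questionnaire route. Both points are correct and limit the consequence to the safety data.

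A reader might go further in three ways that the documents do not support.

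- One might infer that the protocol holds three conflicting risk profiles. Section 5.2 is partly redacted, 8.14 reports general surveillance data and not an estimate for this trial, and pressure injury in 7.4 covers much of the 8.14 list. What remains is a matter of wording.
- One might infer that unblinded assessors will use their discretion to leave events out. Nothing visible shows this, and with no randomized arms there is no differential recording between groups to fear.
- One might infer that all these harms are trivial and sure to be dropped. Section 8.14 does not call them minor, and pressure sores or skin breakdown may well be judged significant and recorded.

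**Conclusion.** The point holds as a contradiction between two recording rules in the current text. Followed as worded, section 10 allows AEs that meet its own definition, including contact-area harms that 8.14 expects, to stay out of the AE data. The direction is known: where the narrower rule is applied, the AE count can only be equal to or lower than the count under 8.14. The amount is not known.

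This rests on two assumptions: that the unseen part of section 10 does not itself resolve the conflict, and that some contact-area events will be judged not clinically significant. The finding does not put the study or its questionnaire-based primary outcome in doubt. It is a worthwhile correction to the safety data, and one best made before participants are fitted, because events that were never entered are hard to recover later.

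**What to change.** State one recording rule, in section 10, and have 8.14 refer to it. Delete the words *clinically significant* from the recording sentence, so that every AE meeting section 10's definition is entered in the CRF with a severity grade. If the sponsor wants to keep the filter for unrelated events, remove it at least for events at mask contact areas and for the complications listed in 8.14. Record clinical significance as an attribute of each event, so that a count restricted to significant events can still be reported alongside the full one.

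The same sentence also sets follow-up, so a plain deletion would widen that too. Separate the two parts and state expressly which events the follow-up requirement covers; that choice is for the sponsor and investigator.

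As a minor wording point, align the risk sentences in 5.2 and 7.4 with the list in 8.14, including allergic reaction.

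The cost is protocol wording, some extra CRF entries for the 40 to 45 participants planned (sections 6.1 and 9.6), and a reported AE count that will look somewhat higher.
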